# English Synopsis

康复医

## I. Title of Study

Development of repetitive transcranial magnetic stimulation (rTMS) combined with machine-assisted bimanual therapy (BT) in upper limb rehabilitation.

## II. Indication

### 1. Inclusion Criteria

- (1) Age 40-80 years;
- (2) First-onset stroke patients;
- (3) Patients diagnosed with cerebral infarction or hemorrhage through CT or MRI;
- (4) Signed informed consent form by the patient and their family;
- (5) Stable physiological parameters;
- (6) Stroke occurred within the last 12 months;
- (7) Patients with unilateral hand function impairment caused by the stroke;
- (8) Upper limb muscle tone (Modified Ashworth Scale, MAS) less than 3 points;
- (9) Able to follow two-step commands.

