## VI. Study Design

- Duration of Treatment

- A. The experiment for establishment of therapeutic environment.

Participants in the experiment for establishment of therapeutic environment underwent 1-3 evaluations. During this experiment, repetitive Transcranial Magnetic Stimulation (rTMS) was employed for brain modulation, involving two sets of stimuli. Each set consisted of initially administering continuous Theta Burst Stimulation (cTBS) to suppress the healthy side (approximately 600 pulses), followed by intermittent Theta Burst Stimulation (iTBS) to enhance the lesion side (600 pulses), totaling approximately 4 minutes (around 1200 pulses). The intensity of iTBS and cTBS is 80-120% of Motor Threshold.

Patients receiving rTMS treatment concurrently underwent machine-assisted bilateral upper limb training. During treatment sessions, patients were instructed to repeatedly perform grasping-opening tasks or engage in bilateral upper limb activities involving simultaneous shoulder and elbow movements while counting down loudly from 300. Upon completion of all training sessions, patients and therapists were required to complete usability and satisfaction analyses to evaluate equipment usability and operational satisfaction.

- B. The experiment for evaluation of therapeutic effects.

Patients will be divided into three groups: a Control group, an rTMS group, and an rTMS+BT group. Each group will receive a 65-minute treatment session, administered once every two days, totaling 10 sessions and completing the entire course within 20 days.

Control group: only received traditional rehabilitation training for 50 minutes and self-stretching training (15 minutes); rTMS group: received rTMS intervention (15 minutes) and 50 minutes of traditional rehabilitation training; rTMS+BT group: received rTMS intervention (15 minutes) along with BT meanwhile and 50 minutes of traditional rehabilitation training.

- Number of Planned Patients

72 participants are expected to be recruited in the trial.

- Investigational Product

1. Robot-assisted palm and finger rehabilitation device

Device name: "RM" Wearable Powered Hand Rehabilitation Device (Non-Sterile)

Manufacturer: Rehabotics Medical Technology Corporation

2. Bilateral proximal/distal upper limb training platform

- (1) The name of proximal upper limb training device: Non-powered upper limb proximal training platform

Manufacturer: Rehabotics Medical Technology Corporation

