- (2) The name of distal upper limb training device: Non-powered upper limb distal training equipment

Manufacturer: developed equipment by the Rehabilitation Department of Chang Gung Hospital

3. Repetitive transcranial magnetic stimulation (rTMS)

Device name: Repetitive transcranial magnetic stimulation (rTMS)

Manufacturer: Apollo Powermag 100, Mag & More, Germany.

- Endpoints

The primary endpoint was evaluated through the Fugl-Meyer Assessment, while secondary endpoints encompassed various measures, including the Modified Ashworth Scale (MAS), Manual Muscle Testing (MMT) for the upper extremity, Action Research Arm Test (ARAT), Brunnstrom Recovery Stage, Instrumental Activities of Daily Living Scale (IADLs). Additionally, participants and therapists responded to the System Usability Scale (SUS) questionnaire, and a Satisfaction questionnaire was administered.

- Criteria for Evaluation

1. Inclusion Criteria

- (1) Demographics and baseline characteristics of the participants were all available.

- (2) Participants completed all treatment sessions.

- (3) Functional assessments of the upper limb were performed at multiple time points: prior to, immediately after, and at 1 and 3 months follow-ups, without any omissions.

- (4) Both participants and therapists completed the System Usability Scale (SUS) questionnaire and the Satisfaction questionnaire.

2. Exclusion Criteria
  - (1) Participants with unforeseen psychological issues or significant changes in health conditions to prevent interference with the analysis.
  - (2) Participants using non-study-related medications that could potentially interfere with the outcomes.

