### ● Statistical Methods

Detailed demographic and medical history records are documented for each subject, including age, gender, time of stroke onset, location of stroke, and types of stroke. The clinical assessment will be conducted by a licensed occupational therapist with experience in treating neurological conditions. Clinical assessment results are being compared between groups using a student-t test. Pre and post-training within each group are being assessed using one-way ANOVA to determine improvement. One-way ANOVA is employed for inter-group comparisons, followed by post-hoc tests. If the data do not follow a normal distribution, non-parametric statistical methods are applied. Correlation analysis is used to explore relationships between clinical assessment results and various factors. Quantitative data are presented as (Mean±SEM), and a 95% confidence interval ( $p<0.05$ ) is considered statistically significant.

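### Patients may enter at MAS 0 and cannot then improve on MAS, yet MAS is an efficacy endpoint in everyone; this dilutes the between-arm effect and muddies the pre/post test

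*Protocol*

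**What the plan says.** Inclusion criterion 8 in the Protocol reads "Upper limb muscle tone (Modified Ashworth Scale, MAS) less than 3 points" and sets no lower limit. The functional requirement, criterion 7, is "Patients with unilateral hand function impairment caused by the stroke", which does not call for raised tone. Criterion 6 gives only a maximum time since stroke of 12 months.

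Under Endpoints in Study Design, "The primary endpoint was evaluated through the Fugl-Meyer Assessment", while "secondary endpoints encompassed various measures, including the Modified Ashworth Scale (MAS" and several other scales. No subset defined by baseline tone is named for MAS.

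Statistical Methods applies the same tests to the clinical assessments generally: a t-test and a one-way ANOVA with post-hoc tests between groups and, within groups, "Pre and post-training within each group are being assessed using one-way ANOVA to determine improvement". Non-parametric methods replace these if the data are not normal. No adjustment for the baseline value is mentioned.

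**The concern.** A MAS of 0 is the bottom of the scale. Someone who starts there can only stay at 0 or rise. Putting these participants into a mean comparison with those who have tone to lose has two consequences.

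- **Between arms.** Participants in whom no fall is possible pull the average treatment difference towards zero. A true reduction in tone among those who have it may be missed or under-reported.
- **Within arms.** The pre/post change nets falls in participants with tone against rises in those without. The resulting average need not describe either group, yet the Protocol uses this test to judge improvement.

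At stake is the reading of one secondary endpoint in a trial of 72 participants in three arms.

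**Working it through.** **Inputs from the Protocol.** Total size: "72 participants are expected to be recruited in the trial". Three arms: "Patients will be divided into three groups: a Control group, an rTMS group, and an rTMS+BT group". Significance level 0.05. MAS below 3 at entry, no lower limit.

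**Assumptions, because the Protocol gives no figure.** Equal allocation, so 72 / 3 = 24 per arm; two-sided testing; share at baseline MAS 0, f = 0.2 to 0.5. The Protocol states no effect size, standard deviation or power, so the 72 cannot be reproduced, and this point does not dispute it.

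**Step 1: between-arm dilution.** Let δ be the treatment effect in participants above 0 and δ₀ the effect in those at 0. The overall mean effect is (1 − f)δ + fδ₀. With δ₀ = 0 it is (1 − f)δ: 80%, 70%, 60% and 50% of δ at f = 0.2, 0.3, 0.4 and 0.5.

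**Step 2: illustrative power.** With 24 per arm, the standardised difference that has 80% power is (1.960 + 0.842) × √(2/24) = 0.81. Suppose that is the effect in participants with tone (SD 1). Normal approximation throughout:

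- A: all participants, SD unchanged: Φ[0.81(1 − f)/√(2/24) − 1.96].
- B: all participants, with baseline-0 participants never changing, so that the SD also shrinks. Variances of change are (1 − f) in control and (1 − f) + f(1 − f) × 0.81² in the treated arm.
- C: only participants above 0, so 24(1 − f) per arm: Φ[0.81/√(2/(24(1 − f))) − 1.96].

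| f | Effect retained in all | A | B | C |
|---|---|---|---|---|
| 0.2 | 80% | 61% | 68% | 71% |
| 0.3 | 70% | 50% | 61% | 65% |
| 0.4 | 60% | 39% | 53% | 58% |
| 0.5 | 50% | 29% | 45% | 51% |

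Under A, restoring 80% power would take 38, 49, 67 and 96 per arm. The restricted analysis loses patients but not power relative to either version of the full one. Its advantage is 10 to 22 points over A and only 3 to 6 points over B.

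**Step 3: within-arm change.** Let a be the mean fall in participants above 0 and w the mean rise in those at 0. The net change is −(1 − f)a + fw. With a = 0.5 grade (assumed):

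| f | w = 0 | w = 0.5 | w/a needed for a net change of zero |
|---|---|---|---|
| 0.2 | −0.40 | −0.30 | 4.0 |
| 0.3 | −0.35 | −0.20 | 2.3 |
| 0.4 | −0.30 | −0.10 | 1.5 |
| 0.5 | −0.25 | 0.00 | 1.0 |

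Full cancellation therefore needs a large share at 0 together with a rise at least as large as the fall elsewhere.

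**Step 4: does Step 3 carry over to the arm comparison?** No. A rise w that is common to all arms is subtracted out. From Step 1, the between-arm effect is zero only if δ₀ = −δ(1 − f)/f, that is, only if treatment itself raises tone in baseline-0 participants.

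**The case against.** **This is detail for an analysis plan.** The SAP is not shown and may handle baseline MAS. That stands as a limit: the Protocol gives no MAS-specific method. But it does state tests for the clinical assessments, and those tests do not suit an ordinal score on which some participants start at the floor. The point corrects a stated method.

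**The non-parametric fallback covers it.** Partly. It would give a rank-type test, but ranking does not let a participant at 0 move down, and it does not condition on baseline.

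**Participants at 0 are still informative.** This stands. If treatment prevents a rise in tone, their data show it. An analysis confined to baseline MAS of at least 1 would discard that, so it should be an addition and not a replacement.

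**Restriction brings regression to the mean.** This stands for the pre/post test. Selecting on a baseline of at least 1 tends to push follow-up scores down, which would flatter a within-arm improvement. The tendency is shared by the arms, so the restricted analysis should be used between arms only.

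**The share at 0 is unknown.** This stands. Criterion 8 does not say which muscle or joint is scored, or how several would be combined, and f depends on that.

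**Stronger readings to avoid.** A reader might infer that the treatment effect on MAS is cancelled, or that the result cannot be interpreted in either direction. Step 4 shows that this does not follow for the arm comparison. A reader might also argue that a higher MAS in flaccid patients is recovery, so that MAS and the Brunnstrom stages conflict. The Protocol only names the Brunnstrom scale; that argument rests on outside knowledge and is not relied on here.

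**Conclusion.** The point holds as dilution. Entry at MAS 0 is permitted, MAS is tested in everyone, and participants at the minimum cannot improve. If treatment leaves them unaffected, the between-arm mean effect falls to (1 − f) of its size: 80% to 50% for an assumed f of 0.2 to 0.5. In the within-arm pre/post test, rises among them offset falls in the others, so that test is ambiguous for MAS.

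The size rests on an assumed f, on no treatment effect at baseline 0, and, for the power figures, on 24 per arm and an effect chosen to give 80% power. The 0 minimum is a property of the instrument that the Protocol does not state. The primary Fugl-Meyer endpoint is unaffected. This is an inexpensive improvement to one secondary endpoint, not a threat to the trial's main conclusion.

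**What to change.** Leave the entry criterion as it is. In Statistical Methods, add for MAS:

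1. Compare arms in all participants with MAS as an ordered outcome, conditional on baseline MAS, for example by proportional odds or a rank test stratified by baseline. Participants who cannot fall are then compared with others in the same position.
2. Add a pre-specified between-arm analysis in participants with baseline MAS of at least 1.
3. Tabulate by arm the number of baseline-0 participants who rise to 1 or more, without labelling the rise as improvement or worsening.
4. State that the within-group pre/post change in MAS will not be read as evidence of efficacy.

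Baseline MAS is already needed for eligibility, so no new measurement is required. The cost is slightly more analysis work and fewer patients in the restricted comparison. The text should be fixed before outcome data are examined, because a tone-based subset chosen afterwards would look selective.

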### 2. Exclusion Criteria

- (1) A history of epilepsy or family history of epilepsy;
- (2) Presence of suicidal tendencies;
- (3) Currently using medications that lower the seizure threshold;
- (4) Pregnant or planning to become pregnant;
- (5) Co-existing neurological diseases (such as multiple sclerosis, other neurodegenerative diseases, meningitis, brain abscess, or meningioma);
- (6) Subjects with uncontrollable migraines caused by elevated intracranial pressure;
- (7) Subjects taking antidepressants who cannot discontinue the medication;
- (8) Subjects with sleep disorders during rTMS treatment;
- (9) Subjects with cerebellar stroke or brainstem stroke;
- (10) Cerebral ischemic disorders resulting from traumatic brain injury;
- (11) Transient ischemic attacks (TIAs);

- (12) History of bleeding tendency and other conditions affecting upper limb function, such as myasthenia gravis, systemic immune neuropathy, severe epilepsy, endocrine system disorders, wearers of external or internal cardiac pacemakers, individuals with metallic implants or orthopedic devices;
- (13) Co-existing severe heart, liver, kidney dysfunction, or other serious physical illnesses;
- (14) Subjects with impaired consciousness who cannot cooperate with examinations or treatments, such as those with mental disorders, or those with intellectual or cognitive impairments, severe dementia;
- (15) Presence of implanted electronic devices in the body;
- (16) Co-existing severe liver, kidney, or hematological disorders;
- (17) Special vulnerable populations;
- (18) Skin disease (e.g., pressure ulcers, trauma, cellulitis, etc.).

### **III. Phase of Development:**

Not applicable.

### **IV. Study Rationale:**

The study aims to establish a therapeutic model that combines Bimanual Therapy (BT) with repetitive transcranial magnetic stimulation (rTMS) to investigate neuroplasticity modulation in stroke patients with upper limb hemiparesis. In the study, inhibitory rTMS will be applied to the unaffected hemisphere, and facilitatory rTMS will be applied to the affected hemisphere during stimulation. Patients will also receive BT concurrently with these rTMS stimulations. Functional assessments of the upper limb will be performed prior to, immediately after, and at 1 and 3 months follow-ups to evaluate rehabilitation outcomes. This study will assess rehabilitation outcomes and explore the associated mechanisms of brain modulation, with the goal of improving clinical applicability.

### **V. Study Objectives:**

This study comprises three main objectives. First, to establish a treatment process and environment for utilizing rTMS to modulate neural activity in patients with upper limb hemiparesis caused by stroke. Second, to investigate the application of inhibitory stimulation, continuous theta burst stimulation (cTBS), to the unaffected hemisphere of the stroke-damaged brain, followed by

facilitatory stimulation, intermittent theta burst stimulation (iTBS), to the affected hemisphere. The intention is to employ the established treatment process in the first part to formulate a clinical treatment model. Third, we will further study functional assessments of the upper limb before treatment, immediately post-treatment, and at 1- and 3-month follow-ups.

## VI. Study Design

- Duration of Treatment

- A. The experiment for establishment of therapeutic environment.

Participants in the experiment for establishment of therapeutic environment underwent 1-3 evaluations. During this experiment, repetitive Transcranial Magnetic Stimulation (rTMS) was employed for brain modulation, involving two sets of stimuli. Each set consisted of initially administering continuous Theta Burst Stimulation (cTBS) to suppress the healthy side (approximately 600 pulses), followed by intermittent Theta Burst Stimulation (iTBS) to enhance the lesion side (600 pulses), totaling approximately 4 minutes (around 1200 pulses). The intensity of iTBS and cTBS is 80-120% of Motor Threshold.

Patients receiving rTMS treatment concurrently underwent machine-assisted bilateral upper limb training. During treatment sessions, patients were instructed to repeatedly perform grasping-opening tasks or engage in bilateral upper limb activities involving simultaneous shoulder and elbow movements while counting down loudly from 300. Upon completion of all training sessions, patients and therapists were required to complete usability and satisfaction analyses to evaluate equipment usability and operational satisfaction.

- B. The experiment for evaluation of therapeutic effects.

Patients will be divided into three groups: a Control group, an rTMS group, and an rTMS+BT group. Each group will receive a 65-minute treatment session, administered once every two days, totaling 10 sessions and completing the entire course within 20 days.

Control group: only received traditional rehabilitation training for 50 minutes and self-stretching training (15 minutes); rTMS group: received rTMS intervention (15 minutes) and 50 minutes of traditional rehabilitation training; rTMS+BT group: received rTMS intervention (15 minutes) along with BT meanwhile and 50 minutes of traditional rehabilitation training.

- Number of Planned Patients

72 participants are expected to be recruited in the trial.

- Investigational Product

1. Robot-assisted palm and finger rehabilitation device

Device name: "RM" Wearable Powered Hand Rehabilitation Device (Non-Sterile)

Manufacturer: Rehabotics Medical Technology Corporation

2. Bilateral proximal/distal upper limb training platform

- (1) The name of proximal upper limb training device: Non-powered upper limb proximal training platform

Manufacturer: Rehabotics Medical Technology Corporation

- (2) The name of distal upper limb training device: Non-powered upper limb distal training equipment

Manufacturer: developed equipment by the Rehabilitation Department of Chang Gung Hospital

3. Repetitive transcranial magnetic stimulation (rTMS)

Device name: Repetitive transcranial magnetic stimulation (rTMS)

Manufacturer: Apollo Powermag 100, Mag & More, Germany.

- Endpoints

The primary endpoint was evaluated through the Fugl-Meyer Assessment, while secondary endpoints encompassed various measures, including the Modified Ashworth Scale (MAS), Manual Muscle Testing (MMT) for the upper extremity, Action Research Arm Test (ARAT), Brunnstrom Recovery Stage, Instrumental Activities of Daily Living Scale (IADLs). Additionally, participants and therapists responded to the System Usability Scale (SUS) questionnaire, and a Satisfaction questionnaire was administered.

- Criteria for Evaluation

1. Inclusion Criteria

- (1) Demographics and baseline characteristics of the participants were all available.

- (2) Participants completed all treatment sessions.

- (3) Functional assessments of the upper limb were performed at multiple time points: prior to, immediately after, and at 1 and 3 months follow-ups, without any omissions.

- (4) Both participants and therapists completed the System Usability Scale (SUS) questionnaire and the Satisfaction questionnaire.

2. Exclusion Criteria
  - (1) Participants with unforeseen psychological issues or significant changes in health conditions to prevent interference with the analysis.
  - (2) Participants using non-study-related medications that could potentially interfere with the outcomes.

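### Usability and satisfaction are rated only once all sessions are finished, so patients who stop early give no rating; if any stop because of the equipment, the patient scores will be too favourable

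*Protocol*

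**What the plan says.** Three places in section VI (Study Design) of the Protocol bear on this.

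- **Timing.** Part A, which sets up the treatment process, states: "Upon completion of all training sessions, patients and therapists were required to complete usability and satisfaction analyses". This is the only time given anywhere for these ratings. No earlier rating is described, and none at the point of stopping.
- **Endpoints.** After the primary and secondary endpoints, the protocol adds that "participants and therapists responded to the System Usability Scale (SUS) questionnaire, and a Satisfaction questionnaire was administered". No time is attached.
- **Criteria for Evaluation.** Inclusion criterion (2) reads "Participants completed all treatment sessions". Criterion (4) reads "Both participants and therapists completed the System Usability Scale (SUS) questionnaire and the Satisfaction questionnaire".

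Exposure differs between the two parts. For part A: "Participants in the experiment for establishment of therapeutic environment underwent 1-3 evaluations". For part B the course is described as "totaling 10 sessions and completing the entire course within 20 days".

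**The concern.** A usability rating is most informative when it comes from people who could not manage the equipment. The task is demanding: magnetic stimulation is given while the patient makes device-assisted movements with both arms and counts backwards aloud. A patient who gives up because stimulation is unpleasant or the device is awkward has direct evidence on whether the process works, yet the stated timing gives that patient no occasion to record it.

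The loss occurs at data collection. If the form is never handed over, no later choice of analysis population can recover the observed answer. That separates this point from the question of who enters the Fugl-Meyer comparison.

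The ratings matter because section V makes establishing the treatment process and environment the first objective. Section V does not itself mention usability, but the System Usability Scale (SUS) and the satisfaction questionnaire are the listed measures that rate the equipment and its operation, and they are the only outcomes named under part A.

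**Working it through.** The protocol gives no figure on this point to reproduce. The check has two steps.

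**1. Does a patient who stops early have any route to a reported rating?**

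- At collection: the rating follows the end of all sessions, and no other occasion is given. The text provides no route.
- At evaluation: suppose a site gave the form at stopping anyway. Criterion (2) admits only those who finished treatment, so if it governs these measures the rating would be dropped.
- The criteria also require the 1- and 3-month assessments, so they fit part B best. Whether they govern part A is not stated.

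Both steps point the same way, and nothing elsewhere in the protocol brings these patients back in.

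**2. What would the omission do to the mean?**

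Let d be the share of equipment users who stop early and are not rated. Let F be the mean among finishers, S the mean that stoppers would have given, and g = F − S.

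- Mean among all users = (1 − d) × F + d × S
- Reported mean minus that mean = F − [(1 − d) × F + d × S] = d × (F − S) = d × g

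The protocol gives neither d nor g, so the values below are assumptions. Here g is the average gap over all stoppers, whatever their reason. Results are in SUS points on the 0 to 100 scale.

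| Share stopping (d) | g = 0 | g = 10 | g = 20 | g = 30 |
|---|---|---|---|---|
| 0% | 0 | 0 | 0 | 0 |
| 5% | 0 | 0.5 | 1.0 | 1.5 |
| 10% | 0 | 1.0 | 2.0 | 3.0 |
| 20% | 0 | 2.0 | 4.0 | 6.0 |
| 30% | 0 | 3.0 | 6.0 | 9.0 |

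The assumed range therefore runs from 0 to 9 points. The shift is upward only if g is positive, that is, if stoppers would have rated lower. The planned total is not split between parts A and B ("72 participants are expected to be recruited in the trial"), so an expected number of unrated patients cannot be given for either part.

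**The case against.** Several objections have force.

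- **Part A is short.** The timing sentence belongs to part A, with 1 to 3 evaluations and no fixed number. Someone who leaves after one may simply count as finished and be rated. This stands: it makes the effect there probably small. It also shows that the trigger is ambiguous. The longer course in part B offers more opportunity to stop, but the protocol does not say that the same timing applies there.
- **An upward bias is not demonstrated.** A reader might infer that the scores are certainly inflated. The documents do not support that. Some patients would have to stop, and those who stop would have to rate lower. Stopping for an unrelated change in health need not lower a rating.
- **Therapists.** A reader might infer that the therapist of a patient who stops is also never asked. The protocol does not say that there is one therapist form per patient, triggered by that patient's completion. A therapist who treats several patients could answer with the stoppers in mind. The point is therefore confined to patient ratings.
- **Limited consequence.** It is tempting to say that the trial could not detect badly tolerated equipment. That goes too far: finishers and therapists can give poor scores, and the number who stop can be counted. The measures are additional, and no threshold or decision rule is attached to them.
- **The document is a synopsis.** The sentence may be mere scheduling, and it does not forbid asking those who stop. That is fair as to intent. But it is the only timing given, and criterion (2) points in the same direction.

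These objections limit the size and certainty of the effect. They do not supply a way for an early stopper's rating to be collected and reported.

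**Conclusion.** The point holds in conditional form. As written, a patient who stops early contributes no usability or satisfaction rating: collection is tied to finishing, and criterion (2) restricts evaluation to finishers. If any patients stop because of discomfort or difficulty with the equipment, the reported patient scores will be too favourable.

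How much too favourable is unknown. The 0 to 9 SUS points above rest wholly on assumed stopping shares of 0 to 30% and assumed score gaps of 0 to 30 points, and should not be read as an estimate for this trial. The timing of these ratings does not affect the Fugl-Meyer primary endpoint. This is a worthwhile, inexpensive improvement to an additional measure and does not threaten the main comparison.

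**What to change.** Two changes in section VI are needed together; the first alone could still leave the new ratings unused.

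1. **Part A timing sentence.** State that the usability and satisfaction questionnaires are given after the last session the patient actually receives, whether or not the course was finished, and at the time of stopping for anyone who stops early. Say whether the same timing applies in part B. This wording also settles who counts as finished when the number of evaluations is not fixed.
2. **Criteria for Evaluation.** Exempt the usability and satisfaction measures from criterion (2). For the same reason, make clear that the full-follow-up requirement in criterion (3) does not remove these ratings.

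Report the scores for everyone who used the equipment at least once, and show separately the number who stopped, their reasons and their scores.

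The cost is a few lines of text and a few minutes with existing forms when a patient stops. The scores may look less favourable, and some who stop may decline to answer, so the number of missing forms should be reported too.

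### Experiment B compares three arms without specifying random or concealed allocation, and the stated between-group tests are unadjusted

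*Protocol*

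**What the plan says.** Under Study Design (section VI), part B is presented as the experiment that evaluates therapeutic effects. Its allocation statement is one sentence: "Patients will be divided into three groups: a Control group, an rTMS group, and an rTMS+BT group". The text then sets out each arm's session content and schedule, but not how a patient comes to be in an arm. The title, rationale, objectives and statistical methods do not call the trial randomised. They mention no sequence generation, concealment, stratification, minimisation or ratio, and they describe no non-random rule either.

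The sample size is given for the whole trial: "72 participants are expected to be recruited in the trial". It is not split between experiments A and B or between arms.

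The inclusion criteria admit "Patients diagnosed with cerebral infarction or hemorrhage through CT or MRI" and set timing by "Stroke occurred within the last 12 months", with no lower limit in days or weeks.

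On the endpoint, "The primary endpoint was evaluated through the Fugl-Meyer Assessment". On analysis, Statistical Methods says "Clinical assessment results are being compared between groups using a student-t test" and also "One-way ANOVA is employed for inter-group comparisons, followed by post-hoc tests". Prognostic data are collected ("Detailed demographic and medical history records are documented for each subject, including age, gender, time of stroke onset, location of stroke, and types of stroke"), but no between-group comparison is said to use them.

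**The concern.** A t-test or one-way ANOVA on the outcome supports a treatment conclusion when the arms are comparable apart from treatment. Random, concealed allocation secures that in expectation. Without it, whoever assigns patients can see time since stroke and stroke type, and the three arms are visibly different packages (self-stretching, rTMS, rTMS with BT), so a preference or a scheduling convenience could influence who goes where. If arms then differ in a factor related to Fugl-Meyer outcome, that difference enters the comparison directly, and the tests as stated do not take it out.

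What is at stake is experiment B's own question: whether a difference between arms reflects rTMS or BT. Allocation is also settled at enrolment. An analysis plan can adjust for measured factors, but it cannot conceal an allocation after the fact, so this belongs in the protocol.

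**Working it through.** **What the text allows.** Set side by side, the sections give:

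- Study Design: three arms, no method of assignment.
- Inclusion Criteria: any time up to 12 months after stroke; infarction or hemorrhage.
- Statistical Methods: between-group t-test and one-way ANOVA with post-hoc tests; onset time, location and type recorded; no stratification and no covariate in the comparison.

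Assigning patients by choice, convenience or device availability would breach nothing in these sections, and the stated tests would not correct for the result.

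**Figure to reproduce.** There is none. The protocol gives 72 without an effect size, SD, power or ratio, and the point does not depend on that number.

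**Illustration of what a bias could do.** Assumptions, none of them from the protocol except the total of 72:

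- all 72 patients are in experiment B in equal arms, so n = 72/3 = 24 per arm;
- one pairwise t-test, two-sided at 0.05 (the protocol gives p<0.05 without stating sidedness);
- no true treatment effect;
- non-random assignment shifts the expected outcome difference by b, in outcome SDs.

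One way to reach b = 0.25 is a 0.5 SD imbalance on a factor correlated 0.5 with the outcome: 0.5 × 0.5 = 0.25.

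Non-centrality = b / √(2/n), with df = 2n − 2. The false-positive rate is P(|T| > critical value) under the non-central t distribution.

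n = 24: √(2/24) = 0.289, df = 46, critical value 2.013.

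- b = 0: 5%
- b = 0.25: non-centrality 0.25/0.289 = 0.87; rate 13.6%
- b = 0.5: non-centrality 0.5/0.289 = 1.73; rate 39.6%

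Because the 72 are not split between experiments A and B, the calculation was repeated with n = 16 per arm (3 × 16 = 48 in B, leaving 24 for A): √(2/16) = 0.354, df = 30, critical value 2.042.

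- b = 0.25: non-centrality 0.71; rate 10.5%
- b = 0.5: non-centrality 1.41; rate 27.8%

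The rate falls with fewer patients only because the test is less sensitive. The bias itself is unchanged.

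**The case against.** The strongest reply is that silence is not evidence. Saying that patients are divided into groups is neutral wording and is also used of randomised trials. The text is headed as an English synopsis, so a fuller protocol may specify randomisation. This stands: a reader might infer that allocation is non-random and that group differences therefore cannot be attributed to treatment, but the document supports neither statement outright. It supports only that the method is unspecified and that the plan as written permits selected arms.

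A reader might also argue from strong spontaneous recovery early after stroke, or say that entry begins on day 0. The protocol does not discuss spontaneous recovery. It sets no numerical lower limit on time since stroke, but it does require stable physiological parameters and the ability to follow two-step commands, and it limits heterogeneity in other ways (first stroke, unilateral hand impairment, no cerebellar or brainstem stroke). The point needs only that arms could differ in time since stroke or stroke type and that these are plausibly prognostic.

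On analysis, the relevant baseline factors are recorded, a correlation analysis with various factors is planned, and covariate adjustment could be set out in an analysis plan that is not shown. So it would be too strong to say that the bias could never be reduced. Still, correlation analysis is not an adjusted comparison, and adjustment reaches only measured factors.

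Finally, the error rates rest on assumed bias sizes, an assumed split of the 72 and a single pairwise test, whereas the plan also names ANOVA with post-hoc tests. That is correct, and they are offered as illustration only.

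**Conclusion.** The point holds in this form: the protocol specifies neither random nor concealed allocation for experiment B, and it compares the arms with unadjusted tests in a population admitted at any time up to 12 months after stroke, with either stroke type. If the arms came to differ in those respects, a group difference could not be attributed to rTMS or BT. If randomisation is in fact used, the defect is one of specification and a short amendment resolves it.

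The size is conditional. Under the stated assumptions, a bias of 0.25 SD takes a nominal 5% error rate to between about 11% and 14%, and 0.5 SD takes it to between about 28% and 40%, depending on whether there are 16 or 24 patients per arm. These figures show how sensitive the comparison is; they do not estimate the bias in this trial. The change should be made before patients are allocated, because later analysis cannot reliably repair selection.

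**What to change.** In part B of Study Design, replace the statement that patients are divided with the following:

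- Participants are randomised 1:1:1 after consent and baseline assessment.
- The list is computer-generated and concealed from enrolling staff, for example by sequentially numbered opaque envelopes.
- Randomisation is stratified by time since stroke, with a cut-point chosen by the sponsor.

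In Statistical Methods, compare the groups on the Fugl-Meyer outcome with a model that includes the stratification factor and the baseline Fugl-Meyer score, in place of the unadjusted t-test and one-way ANOVA.

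If allocation is in fact non-random, say so, label experiment B a non-randomised comparison, and make the adjusted analysis primary.

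The cost is a protocol paragraph, someone not involved in enrolment to prepare the list, and the loss of freedom to schedule arms for convenience. The change itself adds no patients or visits.
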